3.2 Study Outcome Measures

3.2.1 Primary Outcome Measures

1. Occurrence of solicited local and systemic reactogenicity from the time of the study vaccination through 14 days post-vaccination
2. Occurrence of unsolicited non-serious adverse events from the time of the study vaccination through 28 days post-vaccination
3. Occurrence of serious adverse events (SAEs) and new onset chronic medical conditions (NOCMCs) from the time of the study vaccination through approximately Day 181 post vaccination
4. Occurrence of adverse events of special interest through approximately Day 29 post vaccination

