8. Diastolic blood pressure is 55 to 95 mm Hg, inclusive
9. White blood cell count is 3,900 cells/μL or greater³
10. Hemoglobin is 13.0 g/dL or greater (men) or 11.8 g/dL or greater (women)³
11. Platelet count is 135,000 cells/μL or greater³
12. Alanine aminotransferase is less than 45 U/L (women) or 62 U/L (men)³
13. Serum creatinine is less than or equal to 1.25 mg/dL (men) or 1.11 mg/dL (women)³

³Abnormalities in white blood count, hemoglobin, platelet count, alanine aminotransferase, and serum creatinine that are suspected to be due to laboratory anomalies may be repeated once to ensure accuracy; additionally, otherwise eligible subjects with grade 1 abnormalities in these values may be considered for enrollment if, in the opinion of the investigator (or clinician on the 1572), the abnormalities are not clinically significant and do not pose additional risk to the study or the volunteer.

14. Negative serum HIV antibody assay
15. Women of childbearing potential⁴ must use an acceptable contraception method⁵ from 30 days before study vaccination until 60 days after vaccination.

⁴Not sterilized via tubal ligation, bilateral oophorectomy, salpingectomy, hysterectomy, or successful Essure® placement (permanent, non-surgical, non-hormonal sterilization) with documented radiological confirmation test at least 90 days after the procedure, and still menstruating or <1 year has passed since the last menses if menopausal.

⁵Includes, non-male sexual relationships, abstinence from sexual intercourse with a male partner, monogamous relationship with vasectomized partner who has been vasectomized for 180 days or more prior to the subject receiving study vaccination, barrier methods such as condoms or diaphragms/cervical caps **with** spermicide, effective intrauterine devices, NuvaRing®, and licensed hormonal methods such as implants, injectables or oral contraceptives ("the pill").

16. Women of childbearing potential must have a negative urine or serum pregnancy test within 24 hours prior to study vaccination.

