 - Pre-administration reactogenicity assessments will be performed prior to vaccination to establish baseline. Subjects will then receive a single dose of study vaccine via intranasal application. Subjects will be observed in the clinic for two (2) hours to record post-administration reactogenicity and any AE/SAEs will be recorded on the appropriate data collection form prior to discharge from the clinic.
 - Subjects will be provided with a memory aid and other study-related materials to record daily oral temperature, solicited mucosal and systemic reactions, any unsolicited AEs, and concomitant medications. Subjects will be encouraged to take their oral temperature around the same time each day. Subjects must not eat or drink anything hot or cold, or smoke within 10 minutes prior to taking oral temperature. Subjects will be instructed on how to use their memory aid and how to measure and record AEs prior to discharge from the clinic. Subjects will be instructed to notify the study center if they develop any severe reactions after study vaccination. If the site principal investigator or appropriate sub-investigator deems the reaction severe enough, further instructions will be given to the subject on the proper course of action, including a return to the clinic for immediate evaluation if appropriate.

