9.2 Methods and Timing for Assessing, Recording, and Analyzing Safety Parameters

9.2.1 Adverse Events

Adverse Event (AE): International Council for Harmonisation (ICH) E6 defines an AE as any untoward medical occurrence in a patient or clinical investigation subject administered a pharmaceutical product regardless of its causal relationship to the study treatment. An AE can therefore be any unfavorable and unintended sign (including an abnormal laboratory finding), symptom, or disease temporally associated with the use of a medicinal (investigational) product. The occurrence of an AE may come to the attention of study personnel during study visits and interviews of a study recipient presenting for medical care, or upon review by a study monitor.

AEs, including solicited mucosal (vaccination site) and systemic (subjective and quantitative) reactions, not meeting the protocol-defined criteria for SAEs will be captured on the appropriate data collection form and eCRF. Information to be collected for unsolicited non-serious AEs includes event description, date of onset, licensed study physician's assessment of severity and relationship to study product and alternate etiology (if not related to study product), date of resolution of the event, seriousness and outcome. AEs occurring during the collection and reporting period will be documented appropriately regardless of relationship. AEs will be followed through stabilization or resolution.

Any medical condition that is present at the time that the subject is screened will be considered as baseline and not reported as an AE; however, if the severity of any pre-existing medical condition increases, it will be recorded as an AE.

AEs must be graded for severity and assessed for relationship to study product (see definitions below). Adverse events characterized as intermittent require documentation of onset and duration of each episode. The start and stop date of each reported AE will be recorded on the appropriate data collection form and eCRF.

FDA defines an AE as any untoward medical occurrence associated with the use of a drug in humans, whether or not considered drug related.

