9.2.5 Adverse Events of Special Interest

Medically attended wheezing events will be considered adverse events of special interest given the route of study product administration and the nature of the study product (i.e., a live attenuated bacterial vaccine). Though subjects with a history of persistent asthma will be excluded from the study, it is possible that new onset wheezing episodes could occur. These will be evaluated by a study investigator and relatedness to study product will be assessed. Medically attended wheezing events will be evaluated through Day 29.

9.2.6 Procedures to be Followed in the Event of Abnormal Laboratory Test Values or Abnormal Clinical Findings

Solicited mucosal site and systemic reactogenicity events will be documented and reported from the time of study vaccination through 14 days (Day 15) after study vaccination.

Unsolicited, non-serious AEs will be documented from the time of study vaccination through approximately 28 days (Day 29) after study vaccination.

SAEs will be documented from the time of study vaccination through approximately 6 months post vaccination.

[figure not shown]
In addition, if a subject has an abnormal laboratory test value (e.g., complete blood count or serum chemistries), it will be recorded as an AE and will be graded per toxicity table and will be followed up until resolution.

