9.3.1. Solicited Events and Symptoms

Systemic and mucosal (local) solicited adverse events will be collected from the time of study vaccination through 14 days after study vaccination. Systemic events include: fever, chills, fatigue, malaise, myalgia, arthralgia, headache, and hypersensitivity. Mucosal events include: runny nose, stuffy nose/congestion, nasal pain/irritation, epistaxis, sneezing, sinus pressure/pain, sore throat, cough, and shortness of breath. Solicited AEs will be summarized by severity for each day after the study vaccination (Days 1-14 post study vaccination) and as the maximum severity over all 15 days ([Table 38](#), [Table 40](#), [Table 41](#), [Table 42](#), [Table 43](#), [Table 44](#), [Table 45](#), [Table 46](#), [Table 47](#), [Table 48](#), [Table 49](#), [Figure 9](#), [Figure 10](#), [Figure 11](#), and [Figure 12](#).) Severity will be graded on a scale of 0 (absent), 1 (mild), 2 (moderate) and 3 (severe). Grading scales for mucosal and systemic solicited adverse events are presented in [Table 6](#), [Table 7](#), and [Table 8](#), respectively. Additionally, solicited AEs will be analyzed by taking the most severe response over the follow-up period, dichotomizing into a binary variable (none versus mild, moderate, or severe) and using standard techniques, such as exact confidence intervals, to summarize the proportion of subjects reporting each symptom, any local symptom, and any systemic symptom ([Table 39](#).) Summaries of solicited AEs will be presented by treatment arm ([Table 36](#).) The proportion of subjects reporting symptoms will be compared between treatment arms using Chi-square or Fisher's exact test ([Table 37](#).) Solicited adverse events by subject will be presented in [Listing 10](#) and [Listing 11](#).

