9.6. Clinical Laboratory Evaluations

Clinical safety laboratory adverse events will be collected at the time of study vaccination through approximately 7 days after study vaccination (Day 8). Any clinical laboratory parameter that is abnormal at Day 8 will be repeated at the next study visit (or sooner if medically indicated) and followed until normal or stabilization. Parameters to be evaluated include white blood cell count, platelet count, hemoglobin concentration, alanine aminotransferase (ALT), and creatinine. Grading scales for safety laboratory parameters are presented in [Table 9](#).

The number and percentage of subjects with at least one clinical safety laboratory abnormality through Day 8 is presented in the overall summary of adverse events ([Table 34](#).)

The distribution of chemistry results by severity, time point, and treatment group will be presented in [Table 61](#), [Table 62](#), [Table 63](#), [Table 64](#), [Table 65](#), [Table 66](#), and [Figure 14](#). The distribution of hematology results by severity, time point, and treatment group will be presented in [Table 69](#), [Table 70](#), [Table 71](#), [Table 72](#), [Table 73](#), [Table 74](#), [Table 75](#), [Table 76](#), and [Figure 15](#). Descriptive statistics including mean, standard deviation, median, minimum and maximum values by time point, for each laboratory parameter, will be summarized in [Table 67](#) and [Table 68](#) (chemistry) and [Table 77](#), [Table 78](#), and [Table 79](#) (hematology). Changes in laboratory values will be presented in [Figure 16](#), [Figure 17](#), [Figure 18](#), [Figure 19](#), and [Figure 20](#).

Subject visits with abnormal laboratory results, Grade 1 severity or higher, will be presented in [Table 59](#) and [Table 60](#).

[Listing 14](#) and [Listing 15](#) will provide complete listings of individual clinical laboratory results with applicable reference ranges.

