Table 38: Number and Percentage of Subjects Experiencing Solicited Events by Symptom, Maximum Severity, and Treatment Group
 (continued)

Symptom	Severity	BPZE1 10 ⁷ CFU by VaxINator (N=X)			BPZE1 10 ⁹ CFU by VaxINator (N=X)			BPZE1 10 ⁹ CFU by Syringe (N=X)			Placebo by VaxINator (N=X)			All Subjects (N=X)		
		n	%	95% CI	n	%	95% CI	n	%	95% CI	n	%	95% CI	n	%	95% CI
Sneezing	None															
	Mild															
	Moderate															
	Severe															
Sinus pressure/pain	None															
	Mild															
	Moderate															
	Severe															
Sore/irritated throat	None															
	Mild															
	Moderate															
	Severe															
Cough	None															
	Mild															
	Moderate															
	Severe															
Shortness of breath/wheezing	None															
	Mild															
	Moderate															
	Severe															

Note: N = Number of subjects in the Safety Population who received the specified dose. Severity is the maximum severity reported over all solicited symptoms post dosing for each subject.

Table 39: Maximum Severity of Solicited Symptoms Dichotomized, by Symptom and Treatment Group

Symptom	Severity	BPZE1 10 ⁷ CFU by VaxINator (N=X)			BPZE1 10 ⁹ CFU by VaxINator (N=X)			BPZE1 10 ⁹ CFU by Syringe (N=X)			Placebo by VaxINator (N=X)			All Subjects (N=X)		
		n	%	95% CI	n	%	95% CI	n	%	95% CI	n	%	95% CI	n	%	95% CI
Any Symptom	None	x	xx	x.x, x.x	x	xx	x.x, x.x	x	xx	x.x, x.x	x	xx	x.x, x.x	x	xx	x.x, x.x
	Mild or Worse															
	Moderate or Worse															
	Severe or Worse															
Systemic Symptoms																
Any Systemic Symptom	None															
	Mild or Worse															
	Moderate or Worse															
	Severe or Worse															
Fever	None															
	Mild or Worse															
	Moderate or Worse															
	Severe or Worse															
Feverishness	None															
	Mild or Worse															
	Moderate or Worse															
	Severe or Worse															

Table 39: Maximum Severity of Solicited Symptoms Dichotomized, by Symptom and Treatment Group *(continued)*

Symptom	Severity	BPZE1 10 ⁷ CFU by VaxINator (N=X)			BPZE1 10 ⁹ CFU by VaxINator (N=X)			BPZE1 10 ⁹ CFU by Syringe (N=X)			Placebo by VaxINator (N=X)			All Subjects (N=X)		
		n	%	95% CI	n	%	95% CI	n	%	95% CI	n	%	95% CI	n	%	95% CI
Fatigue (tiredness)	None															
	Mild or Worse															
	Moderate or Worse															
	Severe or Worse															

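### The solicited-event rates and placebo contrasts ignore the pre-dose grade, so a symptom that merely continues counts as a reaction; the protocol also conflicts on whether pre-existing laboratory abnormalities are adverse events.

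*SAP*

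**What the plan says.** **Solicited symptoms.** The first primary outcome is "Occurrence of solicited local and systemic reactogenicity from the time of the study vaccination through 14 days post-vaccination" (Protocol 3.2.1). At Visit 1, "Pre-administration reactogenicity assessments will be performed prior to vaccination to establish baseline" (Protocol 7.2). SAP 9.3.1 takes each subject's most severe response over follow-up, "dichotomizing into a binary variable (none versus mild, moderate, or severe", and plans to compare the proportions between arms. The footnotes to Tables 38 and 39 state: "Severity is the maximum severity reported over all solicited symptoms post dosing for each subject". Tables 36 and 37, which carry the rates, intervals and differences from placebo, have no baseline term. The pre-dose grade appears only as a column in the day-by-day Tables 40 to 49 and as a time point in Figure 12.

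**Laboratory values.** Under footnote 3 of Protocol 5.1, "otherwise eligible subjects with grade 1 abnormalities in these values may be considered for enrollment". Inclusion criteria 9 and 11 set only a lower limit for white cells and platelets, although Appendix B also grades increases. Protocol 9.2.6 says of an abnormal value that "it will be recorded as an AE and will be graded per toxicity table". Protocol 9.2.1 says: "Any medical condition that is present at the time that the subject is screened will be considered as baseline and not reported as an AE", with an exception where severity increases. SAP 9.6 adds: "The number and percentage of subjects with at least one clinical safety laboratory abnormality through Day 8" is to appear in Table 34, but that shell has no laboratory row.

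**The concern.** The trial tests no formal hypothesis. Its product is a set of estimates, and Protocol 11.4 says the results will inform the Phase 2b dose, so absolute reactogenicity rates matter in themselves. A rule that scores any post-dose grade mixes new reactions with symptoms the subject brought to the visit.

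Little persistence is required. Post-administration reactogenicity is assessed within the two-hour clinic stay, so a symptom present at dosing need only last until that check. No later step removes it. Listing 10 records alternate etiology for Grade 3 systemic events only, and Listing 11, for local symptoms, has no such column. The pre-dose columns of Tables 40 to 49 are group counts and do not show which post-dose events belong to subjects who were symptomatic beforehand.

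For laboratory values, the two protocol rules would classify the same unchanged Grade 1 value differently, and SAP 9.3 summarises whatever adverse events are reported.

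**Working it through.** **The plan's own figures.** Protocol Table 3 gives 79.4% as the chance of at least one event among 15 subjects at a 10% rate: 1 - 0.90^15 = 79.4%, reproduced. Exact enumeration of the two-sided Fisher test gives 79.3% power for the Table 4 row of 10% v 63% with 15 per arm, which agrees with the stated 80%. The documents give no figure for baseline symptoms.

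**Inputs.** n = 15 per VaxINator arm (Protocol 11.2). b, the proportion with a pre-dose symptom that persists, is an assumption. p, the new-onset rate among subjects free of the symptom at baseline, is illustrative.

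**Absolute rates.** Planned rate = b + (1-b)p, which exceeds p by b(1-p). With p = 50% on vaccine and 30% on placebo:

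| b | Planned rates | Difference | New-or-higher count, no carrier worsens: (1-b)p | Difference |
|---|---|---|---|---|
| 10% | 55% v 37% | 18 points | 45% v 27% | 18 points |
| 20% | 60% v 44% | 16 points | 40% v 24% | 16 points |

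At b = 10% to 20%, 1.5 to 3 of 15 subjects per arm would be events on entry. At p = 10%, the excess b(1-p) runs from 4.5 points (b = 5%) to 27 points (b = 30%).

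**Differences.** The planned difference is (1-b)(p1 - p0). If no symptomatic subject worsens, the new-or-higher count gives the same difference. The full 20 points return only among baseline-free subjects, or if symptomatic subjects worsen as often as others develop new symptoms.

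**Precision.** Fisher power, 15 v 15, for rates borrowed from two Table 4 rows (these are not solicited-event rates):

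| Rates | b | Planned rule | New-or-higher, no carrier worsens |
|---|---|---|---|
| 10% v 63% | 10% | 63% | 71% |
| 10% v 63% | 20% | 49% | 62% |
| 20% v 76% | 10% | 69% | 69% |
| 20% v 76% | 20% | 56% | 58% |

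The gain depends on where the rates lie and can be negligible.

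**Chance imbalance.** With the same underlying b in both arms, two arms of 15 differ by three or more baseline-positive subjects with probability 12% (b = 10%) or 25% (b = 20%). Three extra carriers in one arm move the planned difference by 3(1-p)/15, which is 14 points at p = 30%. If none of them can worsen, they move the new-or-higher difference the other way by 3p/15, which is 6 points. Neither count is immune, and this is a reason to show both.

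**Laboratory.** Of the seven graded directions in Appendix B, only high white cells and high platelets have no entry limit. Assuming 1% to 2.5% of healthy adults lie outside each of those limits, 1 - 0.99^2 = 2.0% to 1 - 0.975^2 = 4.9% would carry such a value, or 0.3 to 0.7 per arm of 15.

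**The case against.** The plan implements the endpoint as written: occurrence after vaccination, not change from baseline. The trial is descriptive and placebo-controlled, and randomization balances carry-over in expectation. The entry rules limit baseline nasal disease: subjects must be in good health, acute illness in the preceding week is excluded, and so are major anatomic nasal abnormality and sinus polyp disease. The recent-steroid exclusion also removes people whose rhinitis currently needs nasal steroids. Persistent mild rhinitis is admitted only because no criterion names it. Pre-dose counts are displayed by grade and arm, and a rise to moderate or severe remains visible in Table 38.

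Most of this stands, and it limits the point. It does not answer it, because the displayed margins cannot be used to remove continuing symptoms from Tables 36 to 39.

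Three stronger readings are tempting. A reader might infer that vaccine-placebo differences are necessarily diluted. The table above shows the difference is unchanged against a new-or-higher count when carriers do not worsen. A reader might infer that laboratory carry-over directly overstates the primary rates. Laboratory abnormality is not a listed primary outcome; it reaches one only if recorded as an unsolicited adverse event, and 9.2.6 can be read subject to the baseline rule in 9.2.1. The SAP also plans baseline graded rows, change from baseline and individual change plots. Finally, a reader might apply 1% to 2.5% to all seven graded directions and expect 7% to 16% of subjects to carry a graded value. Five of those directions fail an inclusion criterion unless the value is Grade 1 and the investigator judges it not clinically significant.

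**Conclusion.** For solicited symptoms the point holds. The collected baseline does not enter the primary rates or the placebo contrasts, and a symptom continuing unchanged from before dosing is counted as a reaction. The overstatement is b(1-p) in each arm: 7 to 14 points at p = 30% if b is 10% to 20%. The true b is unknown and may be smaller, given the entry rules. The effect on comparisons is added noise in small arms, with no expected bias towards either arm. Dilution is conditional, as shown above.

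For laboratory values the supported conclusion is narrower. Protocol 9.2.1 and 9.2.6 conflict over abnormalities already present at screening, entry permits some of them, and no planned display links a subject's screening grade to the Day 8 grade in a table. This is a worthwhile, inexpensive improvement; it does not undermine the planned displays.

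**What to change.** 1. In SAP 9.3.1, define a new-or-worsened solicited event as a post-dose grade higher than the subject's own pre-dose grade for that symptom. Add its count, confidence interval and difference from placebo to Tables 36 and 37, beside the planned rate.
2. Reconcile Protocol 9.2.1 and 9.2.6, and align SAP 9.6, so that laboratory adverse events are counted consistently against the screening grade for the same parameter and direction.
3. Add a within-subject screening-to-Day 8 grade-shift table to the existing laboratory baseline and change displays, and add to Table 34 the laboratory row that SAP 9.6 announces.

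The cost is SAP wording and programming plus a short protocol clarification. All the data are already collected and the planned rate is kept. The downside is two versions of the solicited rate to present and explain.

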14.3.1.2 Unsolicited Adverse Events

Table 50: Summary of Unsolicited Adverse Events by MedDRA System Organ Class and Preferred Term, and Treatment Group*

MedDRA System Organ Class	MedDRA Preferred Term	BPZE1 10 ⁷ CFU by VaxINator (N=X)				BPZE1 10 ⁹ CFU by VaxINator (N=X)				BPZE1 10 ⁹ CFU by Syringe (N=X)				Placebo by VaxINator (N=X)				All Subjects (N=X)			
		n	%	95% CI	Events	n	%	95% CI	Events	n	%	95% CI	Events	n	%	95% CI	Events	n	%	95% CI	Events
Any SOC	Any PT	x	xx	xx, xx	x	x	xx	xx, xx	x	x	xx	xx, xx	x	x	xx	xx, xx	x	x	xx	xx, xx	x
[SOC 1]	Any PT																				
	[PT 1]																				
	[PT 2]																				
[SOC 2]	Any PT																				
	[PT 1]																				
	[PT 2]																				

Note: N = number of subjects in the Safety Population who received the specified dose. This table presents number and percentage of subjects. A subject is only counted once per PT.

Table 51: Unsolicited Adverse Events by MedDRA System Organ Class and Preferred Term, Maximum Severity, Relationship, and Treatment Group - BPZE1 10⁷ CFU by VaxINator*

MedDRA System Organ Class	Preferred Term	Severity	BPZE1 10 ⁷ CFU by VaxINator (N = X)					
			Related		Not Related		Total	
			n	%	n	%	n	%
Any SOC	Any PT	Any Severity	x	xx	x	xx	x	xx
		Mild	x	xx	x	xx	x	xx
		Moderate	x	xx	x	xx	x	xx
		Severe	x	xx	x	xx	x	xx
SOC 1	Any PT	Any Severity	x	xx	x	xx	x	xx
		Mild	x	xx	x	xx	x	xx
		Moderate	x	xx	x	xx	x	xx
		Severe	x	xx	x	xx	x	xx
	PT 1	Any Severity	x	xx	x	xx	x	xx
		Mild	x	xx	x	xx	x	xx
		Moderate	x	xx	x	xx	x	xx
		Severe	x	xx	x	xx	x	xx

Note: N = Number of subjects in the Safety Population.

Tables with similar format:

Table 52: Unsolicited Adverse Events by MedDRA System Organ Class and Preferred Term, Maximum Severity, Relationship, and Treatment Group - BPZE1 10⁹ CFU by VaxINator*

Table 53: Unsolicited Adverse Events by MedDRA System Organ Class and Preferred Term, Maximum Severity, Relationship, and Treatment Group - BPZE1 10⁹ CFU by Syringe*

Table 54: Unsolicited Adverse Events by MedDRA System Organ Class and Preferred Term, Maximum Severity, Relationship, and Treatment Group – Placebo by VaxINator*

Table 55: Unsolicited Adverse Events by MedDRA System Organ Class and Preferred Term, Maximum Severity, Relationship, and Treatment Group - All Subjects*

